13 ANALYSES OF EXPLORATORY ENDPOINTS

The analyses of exploratory endpoints will be performed on the safety population. No statistical inferences will be performed.

13.1 AK Lesions Count

At screening, the Investigator will select and measure the TF (e.g., approximately mid face or an area on the scalp). Each AK lesion within the TF will also be identified with a label. A photograph will be captured using imaging devices to be used to support the location of the same TF identified at screening during the follow-up study visits assessments. At baseline (Day 1), the area of the TF and location of AK lesions in the TF will be confirmed. A baseline photograph is only required in case of any significant change from screening is detected in the TF as per Investigator's judgement or if the quality of the image captured at screening is not appropriate. If no photograph is needed at baseline, then the screening photograph, TF, and AK lesions count will be considered the baseline assessment. At each post-baseline visit, all lesions in the TF will be counted and details on whether the lesion present in the TF is new or an existing lesion at baseline will be recorded in the eCRF.

The absolute number, change from baseline, and percent change from baseline in total number of AK lesions in the TF (i.e., already present at baseline *AND* new) will be analysed descriptively at each visit.

The absolute number, change from baseline and percent change from baseline in AK lesion count for lesions that were already present at baseline in the TF will be summarized at each post-baseline visit using descriptive statistics.

The absolute number and percent change in new AK lesions since baseline in the TF will also be summarized at each post-baseline visit using descriptive statistics. The percent change in new AK lesions since baseline in the TF is defined as:

$$\frac{\text{Number of new AK lesions in the TF}}{\text{Number of AK lesions at baseline}} \times 100$$

A listing of AK lesions count will be provided. Figures of the AK lesions counts (total lesions, lesions that were already present at baseline, and new lesions from baseline) by visit will also be provided.

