### **7.2.4 Rationale for Trial Assessments**

In prior studies, mild to moderate erythema and flaking/scaling were the most frequently observed signs when assessing local tolerability. Local tolerability signs following treatment will be characterized and assessed throughout this study and reported separately from AEs.

Standard safety assessments will be performed throughout the study including the capture of AEs, SAEs, concomitant medications, laboratory testing for hematology, blood chemistry, and urinalysis, PEs and vital signs measures, and ECGs.

Lesion counts in the TF will be performed at Screening, Day 1/Baseline (predose), and at every visit from Day 5 up to Day 57 to evaluate the treatment effect of tirbanibulin ointment 1%, when applied to an area measuring 100 cm^2 on the face or balding scalp.

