#### Treatment Field Identification

The size of the TF must be approximately 100 cm^2.

At Screening, the Investigator will select and measure the anatomical area (eg, approximately mid face or an area on the scalp) and will outline the TF with a marker pen over the skin. Each AK lesion within the TF will be also identified with a label. A photograph will be captured using imaging devices to be used to support the location of the same TF identified at Screening during the follow up study visits assessments.

At Baseline (Day 1), the area of the TF and the number and location of lesions inside it will be confirmed. A baseline photograph is only required in case of any significant change from Screening is detected in the TF as per the investigator judgement or if the quality of the image captured at screening is not appropriate. If no photograph is needed at baseline, then the screening photograph will be considered the baseline assessment. The same field will be located during the study with the aid of imaging software before performing the study assessments. Study Manuals will be provided to describe the image procedures in detail. The number of AK lesions in the TF will be recorded in the eCRF and photographs will be taken according to the schedule in Table 1.

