Weight of study drug packets ^f		X			X				
Standardized photography of the treatment field	X	X ^{a,l}			X	X	X	X	X
AEs ^g	X	X	X		X	X	X	X	X ^h

M-14867-32

Statistical Analysis Plan Status: Version (17 Jan 2023)

Period	Screening*	Treatment		Response Assessment					
		1	2	At home, once-daily self-administration ^m	3	4	5	6	7
Visit(s)									ET/EoS
Day(s)	-28 to -1		1 (Baseline)	2 to 5	5	8	15	29	57
Visit Time Window (days)	None	None			None	±2	±2	±3	±3
Treatment Field location		X ^a		X	X	X	X	X	X
Focused dermatological exam of treatment field									
Local tolerability		X ^a			X	X	X	X	X ^b
Hypo- and hyperpigmentation and scarring		X ^a			X	X	X	X	X ^b
AK Lesion count in the TF	X	X			X	X	X	X	X

Abbreviations: AE=adverse event; AK=actinic keratosis; ECG=electrocardiogram; ET=Early Termination; EoS=End of Study; ICF=informed consent form; TF=treatment field; WOCBP=women of child-bearing potential.

* Patients who require a washout period from prohibited concomitant treatments should be seen and sign the ICF prior to the Screening visit, to ensure the necessary washout before starting treatment. No trial assessments will be performed on that date and the Screening visit will be scheduled according to the washout length required for the specific medication stopped.

^a Assessments/procedures performed before treatment administration. Day 1 evaluation will serve as a Baseline for these assessments.

^b Patients must be in a supine position for 5 minutes prior to ECG.

^c Highly sensitive urinary pregnancy test performed at the clinical trial site.

^d Physical examination to include height, weight, and an assessment of head, eyes, ears, nose and throat, integumentary/dermatological, gastrointestinal, cardiovascular, respiratory, musculoskeletal, neurological systems, and an expanded dermatological examination to cover the sun-exposed areas, where photo-damage is likely. Height is measured only at screening.

M-14867-32

Statistical Analysis Plan Status: Version (17 Jan 2023)

^e On Day 5 patients are to bring all 5 study drug packets back to the site (used and unused) with their respective torn parts in the individual closed zipper storage bag provided in the study kit.

^f All study drug packets will be weighed together in their respective closed zipper storage bag before and after use (including the torn opening part).

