6.3 Baseline

Unless otherwise specified, baseline value will be defined as the last non-missing assessment prior to the first study treatment dose dosing on Day 1 (including unscheduled and repeat assessments). If the last non-missing assessment is performed on the same date as the first study treatment administration and time is not available, the assessment will be considered as baseline, except for adverse events (AEs) not related to a pre-dose assessment and medications starting on the first study treatment dose administration date which will be considered post-baseline.

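### SAP 13.1 takes the Screening lesion count as baseline when no Day 1 photograph is needed, although the protocol carries forward only the photograph and schedules a Day 1 pre-dose count

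*SAP*

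**What the plan says.** SAP 13.1 sets the rule for patients who need no Day 1 photograph: "then the screening photograph, TF, and AK lesions count will be considered the baseline assessment". The same section states when a Day 1 photograph is needed: "A baseline photograph is only required in case of any significant change from screening is detected in the TF as per Investigator's judgement", or when the Screening image is inadequate. No threshold is given for the first condition.

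Protocol Version 2.0, on which the SAP is based, is narrower. Section 10.3.1 (Treatment Field Identification) reads: "If no photograph is needed at baseline, then the screening photograph will be considered the baseline assessment". It mentions neither the treatment field nor the count. It also requires on Day 1 that "the area of the TF and the number and location of lesions inside it will be confirmed"; the matching sentence in SAP 13.1 keeps area and location but omits the number. Protocol 7.2.4 is explicit about timing: "Lesion counts in the TF will be performed at Screening, Day 1/Baseline (predose), and at every visit from Day 5 up to Day 57". The SAP's own Table 1 marks the row "AK Lesion count in the TF" at both Screening and Day 1.

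SAP 6.3 gives the general rule: "baseline value will be defined as the last non-missing assessment prior to the first study treatment dose dosing on Day 1". That rule applies only where nothing else is specified. SAP 3.1 gives the SAP precedence over the protocol. SAP Table 3, which lists changes from the protocol's analyses, does not mention the lesion-count baseline.

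**The concern.** A programmer following the SAP would set aside a later pre-dose count in favour of an earlier one for every patient without a retaken photograph. What decides the baseline date is either the technical quality of an image or an investigator's view of whether a change was large enough. Neither is a sound basis for choosing which count to analyse, and the first has nothing to do with the number of lesions.

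The baseline count is the reference for change and percent change, the denominator of the new-lesion percentage, the split at 8 lesions in SAP 15.1, and an entry in the baseline characteristics table (SAP 10.1). Because eligible counts are small, a difference of one lesion can visibly move a single patient's result.

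**Working it through.** **Which rule governs.** Section 6.3 alone would select the Day 1 pre-dose count whenever it exists. Section 13.1 specifies otherwise, so 6.3 gives way. Protocol 7.2.4 and 10.3.1 point to Day 1, but the SAP prevails. The result is a mixed baseline: Day 1 if a photograph was needed, Screening if not. The Day 1 lesion-count cell in Table 1 lacks the footnote that labels an assessment as pre-dose and as baseline, but protocol 7.2.4 supplies both labels.

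**Age of the carried-forward count.** Screening runs from Day -28 to Day -1 (protocol 10.3.1), so the count can be up to 28 days old at first dose.

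**Weight of one lesion.** The eligible range is 4 to 12 (inclusion criterion 2): 1/12 = 8.3% and 1/4 = 25%.

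**Individual patients.** SAP 7.2 defines percent change as (Y - B)/B × 100. Write S for the Screening count, D for the Day 1 count and Y for the Day 57 total. The counts below are assumed for illustration.

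| S | D | Y | B = S (SAP 13.1) | B = D (Day 1) |
|---|---|---|---|---|
| 4 | 5 | 5 | (5-4)/4 = +25% | (5-5)/5 = 0% |
| 4 | 5 | 1 | (1-4)/4 = -75% | (1-5)/5 = -80% |
| 6 | 7 | 1 | (1-6)/6 = -83.3% | (1-7)/7 = -85.7% |
| 5 | 4 | 4 | (4-5)/5 = -20% | (4-4)/4 = 0% |
| 4 | 5 | 0 | -100% | -100% |

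For the new-lesion percentage (new lesions / baseline × 100, SAP 13.1), one new lesion is 1/4 = 25% on a baseline of 4 and 1/5 = 20% on a baseline of 5. A patient with S = 8 and D = 9 falls in the ≤8 subgroup under SAP 13.1 and in the >8 subgroup from Day 1.

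**Group mean.** If a share r of the Day 1 lesions remains, Y = rD, and the difference between the two percent changes is 100 × r × (D - S)/S. If a fraction f of patients differ by one lesion and have no Day 1 photograph, the mean shifts by ±f × 100 × r × mean(1/S). The documents give neither f nor r, so both are assumed. Screening counts are taken as evenly spread, with both counts kept within 4 to 12.

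- Day 1 one higher (S from 4 to 11): mean(1/S) = 1.1865/8 = 0.1483.
- Day 1 one lower (S from 5 to 12): mean(1/S) = 1.0199/8 = 0.1275.

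| f | r | Day 1 one higher | Day 1 one lower |
|---|---|---|---|
| 5% | 25% | +0.19 points | -0.16 points |
| 10% | 50% | +0.74 points | -0.64 points |
| 30% | 100% | +4.45 points | -3.82 points |

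A positive shift means the Screening baseline makes the lesion reduction look smaller; a negative shift makes it look larger.

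**The case against.** The best defence is that the carried-forward count is usually not out of date. The protocol has the number and location of lesions confirmed on Day 1, and carry-forward applies only when the investigator saw no significant change and the Screening image was adequate. In most such patients the two counts should be the same. That stands, and it limits the size of the problem. It does not justify the rule: where the counts agree, using Day 1 costs nothing, and where they differ, the rule selects the older one.

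The lesion endpoints are also exploratory and descriptive, in a single arm, with no inference planned. That stands too. The largest shifts above require 30% of patients to differ in the same direction with no treatment response.

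Three stronger readings are tempting, and the documents do not support them.

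- A reader might infer that every lesion result is affected. The absolute total count after baseline does not use the baseline, and the percent change for a cleared field is -100% either way.
- A reader might infer that this sentence by itself turns pre-dose lesions into new on-study lesions. New or existing status is not obtained by subtraction. The investigator records it at each visit (protocol 10.4), helped by imaging software and by lesions labelled and photographed at Screening or baseline (protocol 10.6). With no Day 1 photograph, the reference image is the Screening one under the protocol's own rule. Correcting the count alone would not add a later lesion to that image.
- A reader might infer an undeclared departure from a baseline fixed in the protocol's statistical section. That section defines no lesion-count baseline. Sections 7.2.4 and 10.4 do label the Day 1 count as baseline, so the change still belongs in SAP Table 3.

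**Conclusion.** The point holds as a specification error in SAP 13.1 that should be corrected; it is not a threat to the trial's main conclusions. The rule sets aside a scheduled pre-dose count, mixes baseline dates across patients for reasons partly unrelated to lesions, and is not declared as a change. It can affect change and percent change from baseline, the denominator of the new-lesion percentage, and membership of the ≤8 and >8 subgroups.

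In the examples shown, a one-lesion difference moves an individual percent change by between 0 and 25 points. The likely effect on a group mean is small: about 0.6 to 0.7 points in either direction if 10% of patients are affected and half their lesions remain. Those two inputs are assumptions, and the number of patients affected is not given. The wording conflict is certain; its practical impact is not.

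**What to change.** In SAP 13.1:

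1. Limit the carry-forward to the photograph by removing the treatment field and the lesion count from that sentence.
2. Define the baseline lesion count as the Day 1 pre-dose count, using Screening only if Day 1 is missing, which is what 6.3 already gives.
3. State that new versus existing status is judged against the lesions present at that same Day 1 baseline, so that a lesion first seen between Screening and Day 1 is not reported as new on study. Without this step, a corrected count could be paired with a Screening reference image that does not show the extra lesion.

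If the sponsor prefers to keep the present rule, it should be listed and justified in SAP Table 3.

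The cost is a few sentences in the SAP. The Day 1 count is already scheduled, so the count baseline needs no new data. Step 3 may require checking how sites classified any lesion first seen between Screening and Day 1.

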14 ANALYSES OF SAFETY AND TOLERABILITY ENDPOINTS

The analyses of safety and tolerability endpoints will be performed on the safety population.

14.1 Local Tolerability Assessment

Local tolerability is assessed based on the review of the following signs in the treatment field: erythema, flaking/scaling, crusting, swelling, vesiculation/pustulation, and erosion/ulceration and will be evaluated both individually and as a composite score (total of the 6 individual scores ranging from 0 to 18). These signs will be graded as: 0=absent, 1=mild (slightly, barely perceptible), 2=moderate (distinct presence), and 3=severe (marked, intense). If one or more individual score is missing, the composite score will be set as missing.

The maximum local tolerability signs composite score across visits will be derived as the maximum local tolerability assessment (LTA) composite score observed post-baseline for a patient. The maximum local tolerability of individual signs across visits will be derived as the maximum LTA of an individual sign observed postbaseline for a patient.

Descriptive statistics will be presented for local tolerability signs composite score by visit, and for maximum local tolerability signs composite score across post-baseline visits. Frequency and percentages by visit of patients presenting any individual and composite local tolerability signs and associated CI based on exact Clopper-Pearson method will be presented. The presence of any individual and composite local tolerability sign is defined by a score of >0. Frequency and percentages by visit for specific local tolerability individual signs results and maximum local tolerability of individual signs across post-baseline visits will also be provided.

The 95% CI will be presented for the median of the maximum local tolerability composite score.

Figures presenting the number of patients with each local tolerability individual sign (absent/mild/moderate/severe) by visit, and a figure presenting the mean local tolerability composite score by visit will be produced.

The time to maximum LTA score for each individual sign and the time to maximum LTA composite score will be calculated as the time (in days) from the first dose of study treatment to the time of the first occurrence of the maximum LTA score observed post-baseline for each individual sign and composite score, respectively. That is, for each individual sign, time to maximum LTA, in days, will be calculated as follows:

(Date of first post-baseline occurrence of maximum LTA score for an individual sign – Date of first dose)

Time to maximum composite LTA, in days, will be calculated as follows:

(Date of first post-baseline occurrence of maximum composite LTA score – Date of first dose)

If a patient's maximum composite/individual sign LTA score stays at 0 throughout the study, the patient will be considered censored at his last LTA score observation. The time to maximum composite/individual sign LTA will be analyzed using Kaplan Meier estimation, overall and by strata as applicable. The Kaplan Meier estimates will include the 25th, 50th (median), and 75th percentiles along with their 95% CIs. The standard errors (SE) will be computed using the Greenwood's formula. The CI for the median will be calculated as per Brookmeyer and Crowley and the CIs for the 25th and 75th percentiles will be calculated using the log-log transformation.

Survival curves will also be presented and all local tolerability assessments will be listed.

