### *Efficacy and Safety*

The efficacy and safety studies included two Phase 3 double-blind, vehicle-controlled, randomized trials, KX01-AK-003 (N=351) and KX01-AK-004 (N=351), that were conducted in the US to evaluate the efficacy and safety of tirbanibulin ointment 1% compared to vehicle ointment in patients with AK on face or balding scalp. Tirbanibulin ointment 1% once daily for 5 days was effective in the treatment of AK on either the face or balding scalp, with statistically significantly higher rates of complete and partial clearance at Day 57 in the treated field as compared to control vehicle (complete clearance, 49% vs 9%, respectively). Treatment-related adverse events (AEs) were few (16% vs 10%, respectively) and consisted of mostly transient mild to moderate application site pruritus and pain that required no treatment; there were no treatment-related SAEs. Signs assessing local tolerability were mostly mild to moderate erythema and flaking/scaling. Mean composite scores for local tolerability signs peaked at Day 8 and were mostly resolved by Day 29.

The safety of treating larger AK fields (>25 cm^2) was evaluated in a Phase 1, maximal usage trial (MUsT), in which tirbanibulin ointment 1% was applied to an area measuring 100 cm^2 on the face or balding scalp in 28 patients with AK. The most frequently reported treatment-related AEs were application site pruritus and application site pain. All AEs were mild or moderate in intensity; no severe AEs were reported. The most frequently reported local tolerability signs were erythema and flaking/scaling. Most local tolerability signs were mild or moderate, with severe erythema and flaking/scaling reported in 14.3% of patients each. Local tolerability sign composite scores peaked around Day 7 to 8 and were mostly resolved by Day 29.

A detailed description of the completed clinical studies is provided in the Athenex KX2-391 Ointment 1% (tirbanibulin) Investigator's Brochure.

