### **6.2 Endpoints**

#### **6.2.1 Safety Endpoints**

##### *Safety Endpoints*

- Local Tolerability Assessment:
  - Local tolerability score by visit (0-3) for each individual sign (erythema, flaking/scaling, crusting, swelling, vesiculation/pustulation, and erosion/ulceration)
  - Maximum local tolerability score post baseline through all the visits for each individual sign
  - Time to maximum local tolerability score for each individual sign

- Local tolerability signs composite score (0-18) by visit, defined as the sum of the scores graded from 0 to 3 on all six individual tolerability sign categories
- Maximum local tolerability signs composite score post baseline through all the visits
- Time to maximum local tolerability composite score
- Pigmentation and scarring in the TF through all the visits
- TEAEs, TESAEs, adverse events of special interest (AESIs), clinical laboratory data, and other safety assessments (vital signs, physical examinations [PEs], electrocardiograms [ECGs])

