7 DATA HANDLING

7.1 Missing Data

No imputation will be made for missing data. See [Appendix 2](#) for handling of completely or partially missing dates and time for prior and concomitant medications and adverse events.

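### Carrying the missing-composite rule of SAP 14.1 into the maximum composite, its timing and composite presence can report less than the recorded signs already prove (minor, cheap to fix)

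*SAP*

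**What the plan says.** SAP 14.1 defines the composite as the "total of the 6 individual scores ranging from 0 to 18", with each sign graded from 0 (absent) to 3 (severe). On incomplete scoring it says: "If one or more individual score is missing, the composite score will be set as missing". The maximum is "the maximum local tolerability assessment (LTA) composite score observed post-baseline for a patient". Time to maximum is the date on which that maximum first occurs minus the date of first dose. A patient whose maximum stays at 0 is censored in the Kaplan-Meier analysis. Presence of a sign, individual or composite, means a score above 0.

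The endpoint comes from Protocol 6.2.1: "Maximum local tolerability signs composite score post baseline through all the visits". It serves the primary safety and tolerability objective. Time to maximum composite is listed there too.

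On missing data in general, SAP 7.1 says "No imputation will be made for missing data", and Protocol 11.9 says the same. SAP 7.3 chooses between assessments in a window by distance from the target day. SAP 7.4 lets a repeat replace the original. Neither considers whether all six signs were scored. No bound, sensitivity analysis or count of partly scored assessments is planned.

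**The concern.** No sign can score below 0, so the sum of the signs that were recorded can never exceed the true composite. It is a proven lower bound. Once the composite is set to missing, that bound is lost to every output built on the composite.

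For a by-visit mean this costs one observation. For a maximum the effect has a direction: removing a visit can lower the maximum or leave it unchanged, but never raise it. In a safety trial that is the unfavourable direction. The visit that matters most is Day 8. In the earlier trial on 100 cm², Protocol 5.1.5 reports: "Local tolerability sign composite scores peaked around Day 7 to 8". If the Day 8 composite is lost, time to maximum moves to another visit, earlier or later. If the remaining complete composites are all 0, the patient meets the censoring rule despite having recorded signs.

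Composite presence is affected in the same way. One recorded sign above 0 proves that the composite is above 0, but a missing composite cannot be counted as present.

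**Working it through.** **Inputs.** From SAP 14.1: six signs scored 0 to 3, the missing-composite rule, the maximum over observed composites, and time as date of maximum minus date of first dose. From SAP 5: about 100 treated patients. From SAP Appendix 1: percentages use the number of patients in the population unless otherwise specified. The rate of unscored signs is not in the documents and is assumed below.

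**The plan's own figure.** Composite range: 6 × 0 = 0 to 6 × 3 = 18. This reproduces.

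**Bounds for a partly scored assessment.** Lower bound = sum of recorded signs (unscored sign taken as 0). Upper bound = that sum + 3 for each unscored sign.

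**Example 1 (constructed).** Day 5 complete, composite 3. Day 8 recorded 3 + 3 + 1 + 0 + 0 = 7, one sign unscored. Day 15 complete, composite 2. Later visits are no higher.

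- SAP rule: Day 8 composite missing; maximum = max(3, 2) = 3; time = 5 − 1 = 4 days.
- From the recorded signs: Day 8 composite lies between 7 and 7 + 3 = 10, so the true maximum is 7 to 10; time = 8 − 1 = 7 days.
- Understatement: at least 7 − 3 = 4 points, at most 10 − 3 = 7.

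**Example 2 (constructed), time shifting later.** Complete composites: Day 5 = 4, Day 15 = 5, Day 29 = 1, Day 57 = 0. Day 8 recorded 3 + 3 + 2 + 1 + 1 = 10, one sign unscored.

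- SAP rule: maximum 5, time 15 − 1 = 14 days.
- From the recorded signs: maximum 10 to 13, time 7 days.

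**Composite presence.** With a population denominator of 100, each patient with a recorded sign above 0 but a missing composite lowers the percentage at that visit by 1/100 = 1 percentage point.

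**How often it could happen.** Assume each sign is unscored independently with probability q. The composite is missing at a visit with probability 1 − (1 − q)^6, and at one or more of the five post-baseline visits with probability 1 − (1 − q)^30.

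| Assumed q | Missing at a given visit | Missing at one or more of five visits |
|---|---|---|
| 0.1% | 0.6% | 3.0% |
| 0.5% | 3.0% | 14.0% |
| 1% | 5.9% | 26.0% |
| 5% | 26.5% | 78.5% |

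These rates are illustrative. If unscored signs cluster in the same assessments, fewer visits are affected for the same q. Only a partial sum above every complete composite changes the maximum in a provable way.

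**Effect on the mean maximum.** Suppose a share of patients is understated as in Example 1, by 4 to 7 points:

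- 0% of patients: no effect.
- 1%: 0.01 × 4 = 0.04 to 0.01 × 7 = 0.07 points.
- 5%: 0.05 × 4 = 0.20 to 0.05 × 7 = 0.35 points, on a scale of 0 to 18.

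**The case against.** **The rule follows the protocol.** The protocol defines the composite as a sum over all six signs and rules out imputation, so a five-sign sum is not the defined score. This stands for the by-visit composite. It does not require that a proven lower bound be ignored when a maximum is taken.

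**Nothing severe is hidden.** A reader might infer that a visit with severe signs drops out of the safety report. The documents do not support that. By-visit frequencies, maxima and times for each sign are derived separately, and all assessments are listed. In Example 1 the two scores of 3 at Day 8 still appear as severe. For the same reason, only the composite version of presence is affected, not presence of an individual sign.

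**It may hardly ever happen.** The six signs are graded in one examination, and the protocol provides for database checks and queries. Missingness near zero is plausible, although the documents do not say the fields are mandatory. The trial is also single-arm and descriptive, and its sample size does not rest on the maximum composite. This limits the severity.

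**The remedy could bias upward.** Counting partly scored visits only when the answer is yes makes inclusion depend on the outcome. That is a fair warning if the denominator is patients with a known answer. With the fixed population denominator of Appendix 1, counting proven cases moves the percentage toward the truth and cannot overshoot it. The denominator must therefore be stated.

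**A floor is an imputed 0 under another name.** Numerically it is the same. But the floor never exceeds the true maximum and is never further from it than the planned value. What stands is that the summary would mix exact values with bounds, and that a patient's maximum could exceed every composite in the by-visit summary. Hence the flag, or a separate sensitivity row.

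**Conclusion.** The point holds for three outputs: the maximum composite, the time to it, and composite presence. That the reported value can fall below one the data prove was reached follows from the SAP's own definitions and needs no assumption. The size does need one. For an affected patient such as Example 1 the shortfall is 4 to 7 points. Across the trial it is zero if every assessment is fully scored, and stays below half a point on the mean if at most 5% of patients are affected to that degree.

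A reader might go further and conclude that the SAP departs from the protocol, or that the maximum composite will be materially wrong. Neither is supported: the by-visit rule agrees with the protocol's definition, and no rate of unscored signs is given. This is a minor point, worth making because the correction is cheap.

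**What to change.** In SAP 14.1:

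1. Keep the by-visit composite mean on complete scores.
2. Count composite presence as yes whenever any recorded sign is above 0, and state the denominator.
3. For the maximum composite and its time, use the sum of recorded signs as a flagged lower bound when it exceeds every complete composite for that patient. If the sponsor sees this as conflicting with SAP 7.1, leave the planned maximum and show the bound as a labelled sensitivity row beside it, with an upper bound that sets the unscored sign to 3.
4. Report the number of partly scored assessments. If it is zero, the matter is closed.

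List the change in SAP section 16. The cost is a few lines of text and code, a footnote, and a few values in the maximum that are bounds and not exact scores.
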